7.3.3. Discontinuation from the Study

Patients will be discontinued from the study in the following circumstances:

- enrollment in any other clinical trial involving an IP or enrollment in any other type of medical research judged not to be scientifically or medically compatible with this study
- the investigator decides that the patient should be discontinued from the study
- the patient, for any reason, requires treatment with another therapeutic agent that has been demonstrated to be effective for treatment of the study indication, discontinuation from the study occurs prior to introduction of the new agent
- the patient or the patient's designee requests that the patient be withdrawn from the study
- Lilly stops the study or stops the patient's participation in the study for medical, safety, regulatory, or other reasons consistent with applicable laws, regulations, and GCP

Patients who are discontinued from study participation will not be followed for PD or survival.

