7.3. Discontinuation

The reason for discontinuation and the date of discontinuation will be collected for all patients. All enrolled patients who discontinue, regardless of whether or not they received study treatment, will have procedures performed as shown in the Study Schedule ([Attachment 1](#)).

Patients who are discontinued from study treatment early will have follow-up procedures performed as shown in the Study Schedule ([Attachment 1](#)).

If a patient withdraws informed consent, he or she must not be contacted unless he or she has explicitly provided permission and consent. Lilly may continue to use previously collected medical research data prior to the withdrawal consistent with the original authorization.

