7.3.2. Discontinuation of Study Therapy

Patients will be discontinued from the study treatment in the following circumstances:

- Enrollment in any other clinical trial involving a study drug or enrollment in any other type of medical research judged not to be scientifically or medically compatible with this study.
- The patient, for any reason, requires treatment with another therapeutic agent that has been demonstrated to be effective for treatment of the study indication; discontinuation from study therapy occurs prior to introduction of the new agent.
- Investigator/Physician Decision
 - The investigator/physician decides that the patient should be withdrawn from the study due to an intercurrent illness or change in the patient's condition that renders the patient unsuitable for further treatment in the opinion of the investigator.

- Any study therapy-related event that is deemed life-threatening, regardless of grade, warrants discontinuation of that therapy and/or discontinuation from all therapy if appropriate in the opinion of the investigator.
- If the patient has progressive disease (PD, confirmed by irRECIST or unconfirmed but with clinically worsening/deterioration [Section 10.1.5.1 and Table JFCQ.10.1]).
- Any event(s) which would require a given study therapy to be modified by more than 2 dose reductions or to be held for more than 6 weeks following Day 1 of the most recent cycle warrants discontinuation of that therapy.
- The patient becomes pregnant during treatment.
- Patient Decision
 - The patient or patient's designee (for example, parents or legal guardian) requests to be withdrawn from the study or study treatment.
- Sponsor Decision
 - The sponsor stops the study or stops the patient's participation in the study for medical, safety, regulatory, or other reasons consistent with applicable laws, regulations, and good clinical practices (GCP).
- The patient is significantly noncompliant with study procedures and/or treatment.
- An unacceptable AE/toxicity (for example, a persistent moderate toxicity that is intolerable to the patient).
- A Grade 3 to 4 IRR, and potentially other drug-related AEs, as specified in Section 9.4.1 below.

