7.3.4. Patients who are Lost to Follow-Up

A patient will be considered lost to follow-up if he or she repeatedly fails to return for scheduled visits and is unable to be contacted by the study site. Site personnel, or an independent third

party, will attempt to collect the vital status (that is, alive or dead) for all patients who are lost to follow-up, including patients who do not receive study treatment within legal and ethical boundaries. Site personnel, or an independent third party, may search public sources for vital status information. If the patient's vital status is determined, the vital status will be documented and the patient will not be considered lost to follow-up.

Lilly personnel will not be involved in any attempts to collect vital status information.

7.3.5. *Discontinuation of Study Sites*

Study site participation may be discontinued if Lilly, the investigator, or the ethical review board (ERB) of the study site judges discontinuation of study site participation necessary for medical, safety, regulatory, ethical, or other reasons consistent with applicable laws, regulations, and GCP.

7.3.6. *Discontinuation of the Study*

The study will be discontinued if Lilly judges discontinuation of the study necessary for medical, safety, regulatory, ethical, or other reasons consistent with applicable laws, regulations, and GCP.

8. Investigational Plan

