Long-term follow-up begins the day after short-term follow-up is completed and continues until the patient's death or overall study completion.

[figure not shown]
- **Continued Access Period:** begins after study completion and ends at the end of trial. During the continued access period, patients on study treatment who continue to experience clinical benefit and no undue risks may continue to receive study treatment until one of the criteria for discontinuation is met. The continued access period includes continued access follow-up.

- Continued access follow-up: begins the day after the patient and the investigator agree that the patient will no longer continue treatment in the continued access period and lasts approximately 30 days.

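### Protocol 7.3.3 ends survival follow-up for a patient who needs another effective agent, whereas 10.1.2 continues it until death or study completion

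*Protocol*

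**What the plan says.** Protocol 7.3.3 lists the circumstances in which a patient leaves the study. One is the need, for any reason, for another agent demonstrated to be effective in the indication, in which case "discontinuation from the study occurs prior to introduction of the new agent". Another is "enrollment in any other clinical trial involving an IP or enrollment in any other type of medical research" judged incompatible with this one. A closing sentence covers the whole list: "Patients who are discontinued from study participation will not be followed for PD or survival".

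Protocol 7.3.2 gives nearly the same two triggers as reasons to stop treatment. For the new agent, "discontinuation from study therapy occurs prior to introduction of the new agent". For other research, the entry begins "Enrollment in any other clinical trial involving a study drug or enrollment in any other type of medical research".

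Protocol 10.1.2 deals with the period after treatment stops. Once a patient progresses or starts a new anticancer therapy, scans are no longer required, but contact continues about every 3 months until death or overall study completion. Section 8.1 is unqualified: "Long-term follow-up begins the day after short-term follow-up is completed and continues until the patient's death or overall study completion". Attachment 1 schedules survival contacts every 3 months to the same end point.

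SAP 5.5.6.1 censors OS at the last contact before the data cutoff. SAP 5.5.6.2 does not censor PFS at new therapy in the main analysis. The sensitivity analysis in Table JFCQ.5.2 does, unless progression or death follows within 14 days.

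**The concern.** A patient who starts a proven next-line agent is subject to two follow-up rules. Under 7.3.3 the patient leaves before the first dose of that agent and vital status is no longer sought. Under 10.1.2 the patient stays in survival follow-up. Nothing in 7.3.3 limits its closing sentence to, for example, patients who withdraw consent, so two sites could act differently and both cite the protocol.

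The endpoint at stake is mainly OS. If deaths after next-line start are not collected, OS is censored at a moment tied to the course of the disease and to fitness for more treatment. That makes independent censoring doubtful for the Kaplan-Meier estimates, including the 6-month and 1-year OS rates planned in the SAP. For PFS, a patient who switches without progression and later dies should count as an event in the main analysis, and that death would be missed.

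**Working it through.** **1. The texts side by side, for a patient who starts a new effective agent.**
- 7.3.3: off the study before the agent starts, with no follow-up for progression or survival.
- 7.3.2: off study therapy only.
- 10.1.2: scans stop, and contact continues about every 3 months to death or study completion.
- 8.1 and Attachment 1: survival follow-up to death or study completion, with no exception for this event.

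Scans are not in dispute, because 10.1.2 also stops them at new therapy. The conflict is over survival follow-up. A lesser conflict concerns 10.1.3.2, which requires the first progression date on the CRF even when it falls after a new therapy has started.

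**2. The same comparison for enrollment in another trial.** 10.1.2 does not mention this trigger. What remains is the overlap between 7.3.2 and 7.3.3 and the general rules in 8.1, 8.1.1 and Attachment 1.

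**3. Primary endpoint.** Inputs from Protocol 12.1 and SAP 5.5.5: n = 54, null ORR 20%, research ORR 35%, one-sided exact binomial test at 10%.
- P(X ≥ 15 | 0.20) = 0.107, above 0.10.
- P(X ≥ 16 | 0.20) = 0.060, so rejection needs 16 responders.
- P(X ≥ 16 | 0.35) = 0.834, which reproduces the stated 83%.

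Responses after the start of new anticancer therapy are already excluded (Protocol 10.1.3.2, SAP 5.5.5). Ending follow-up at that point therefore changes none of these figures.

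**4. How many patients could be affected.** The documents give no next-line rate for this population. Protocol 5.2 reports later anticancer therapy in 45% and 47% of the two arms of the first-line phase 3 squamous trial. Borrowing that as an assumption: 54 × 0.45 = 24.3 and 54 × 0.47 = 25.4 patients. Over an assumed 20% to 60%: 54 × 0.20 = 10.8 to 54 × 0.60 = 32.4. These are patients exposed to the conflicting rule, not deaths lost.

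**5. Illustration of deaths lost per 54 patients.** All inputs are assumed:
- PFS exponential with median 4 months; 15% of PFS events are deaths.
- Next-line therapy starts 0.7 months after progression in 30% to 60%; 5% to 15% switch without progression.
- Median survival is 6 to 12 months from new therapy, and 3 to 6 months from progression without it.
- Administrative cutoff is uniform from 6 to 16 or 6 to 19 months.

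If 7.3.3 were applied to every patient starting new therapy, 4.3 to 16.2 deaths would be lost out of 24 to 34. The loss scales with the share of patients to whom it is applied: at 10%, 0.10 × 4.3 = 0.4 to 0.10 × 16.2 = 1.6. The shift in median OS at full application runs from −0.85 to +3.11 months, so its sign depends on the assumptions.

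These ranges are not bounds. Letting the PFS median run from 2 to 8 months, the death share from 5% to 30% and the lag from 0.3 to 1.5 months widens the loss at full application to about 2 to 21 deaths, out of about 16 to 44.

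**6. PFS under the inputs first listed in step 5.** At full application, 1.0 to 5.1 of 41 to 46 events are lost, and median PFS moves by at most 0.35 months.

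**The case against.** The best defence is that 7.3.3 is meant narrowly, for patients who leave the study altogether, and that the rest of the protocol shows this. Section 7.3 opens with: "All enrolled patients who discontinue, regardless of whether or not they received study treatment, will have procedures performed as shown in the Study Schedule". Section 8.1.1 has investigators follow the schedule for all patients until told that the study is complete. Section 9.6 prohibits no therapy in post-treatment follow-up. Protocol 12.2.4.1 and SAP 5.7.3 tabulate post-discontinuation therapies, which presupposes that patients receiving them are still observed. For patients lost to follow-up, 7.3.4 says that site staff or a third party "will attempt to collect the vital status (that is, alive or dead) for all patients who are lost to follow-up". That does not conflict with 7.3.3, since it concerns patients who cannot be reached, but it does suggest that survival data are wanted. All this makes the narrow reading the likelier intention and lowers the practical risk. It does not remove the contradiction, because 7.3.3 states its rule without limit.

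Three further points stand in part. The 7.3.3 trigger (an agent of proven efficacy in the indication) is narrower than the 10.1.2 trigger (any new anticancer therapy), so the two groups overlap without being identical. The PFS consequence is small, because scans stop at new therapy under either reading and the planned sensitivity analysis already censors there. And Protocol 8.2 calls the outcome hypothesis generating only, which limits what rests on OS.

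A reader might infer that entering another trial produces the same direct contradiction. The documents do not support that. The texts on the other side are general defaults, and 7.3.3 could be read as the specific exception to them.

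**Conclusion.** The contradiction is real for a patient who requires another effective agent: 7.3.3 ends survival follow-up, while 10.1.2, 8.1 and Attachment 1 continue it. For enrollment in another trial it is an ambiguity. The wording should be fixed, but the point does not threaten the primary result. ORR is unaffected, and OS and PFS are secondary and descriptive.

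A reader might also infer that OS will be biased in a known direction, or that the number of deaths lost can be bounded. Neither follows. The documents do not say how many patients receive next-line therapy, how many switch without progression, or how often a site would apply 7.3.3. The follow-up length in the illustration is assumed as well. The planned last visit in the synopsis is June 2017, but this protocol version was approved in September 2018, and Protocol 12.1 allows some Part B efficacy to be updated at the Part C analysis. What can be said is that applying 7.3.3 as written would censor OS near next-line start, which is potentially informative, and would drop some deaths from the main PFS analysis.

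**What to change.** Reconcile 7.3.3 with 7.3.2, 8.1, 10.1.2 and Attachment 1. State that starting a new anticancer therapy, including within another trial, does not by itself end the survival follow-up already scheduled, unless the patient withdraws consent to that follow-up. This concerns data collection only and proposes no rule on treatment.

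As a separate minor point, reconcile the wording of 9.6 (patients needing a disallowed treatment are removed from the trial) and 9.7 (significantly noncompliant patients are discontinued from the study) with 7.3.2 and 7.3.3. Section 7.3.2 lists noncompliance as a reason to stop treatment. Which rule should apply is for the sponsor to settle.

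The cost is protocol wording. The 3-monthly survival contacts are already in Attachment 1, so no visits, patients or analyses are added.

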7.3.4. Patients who are Lost to Follow-Up

A patient will be considered lost to follow-up if he or she repeatedly fails to return for scheduled visits and is unable to be contacted by the study site. Site personnel, or an independent third

party, will attempt to collect the vital status (that is, alive or dead) for all patients who are lost to follow-up, including patients who do not receive study treatment within legal and ethical boundaries. Site personnel, or an independent third party, may search public sources for vital status information. If the patient's vital status is determined, the vital status will be documented and the patient will not be considered lost to follow-up.

Lilly personnel will not be involved in any attempts to collect vital status information.

7.3.5. *Discontinuation of Study Sites*

Study site participation may be discontinued if Lilly, the investigator, or the ethical review board (ERB) of the study site judges discontinuation of study site participation necessary for medical, safety, regulatory, ethical, or other reasons consistent with applicable laws, regulations, and GCP.

7.3.6. *Discontinuation of the Study*

The study will be discontinued if Lilly judges discontinuation of the study necessary for medical, safety, regulatory, ethical, or other reasons consistent with applicable laws, regulations, and GCP.

8. Investigational Plan

8.1. Summary of Study Design

[figure not shown]
Study I4X-MC-JFCQ is an open-label, multicenter Phase 1b study with an expansion cohort to investigate necitumumab in combination with pembrolizumab in approximately 78 patients with Stage IV NSCLC (AJCC Staging Manual, 7th edition).

The study consists of 3 parts:

- Part A: Dose-escalation part with increasing doses of necitumumab (initially 600 mg and then 800 mg on Days 1 and 8 Q3W) to determine a recommended dose for necitumumab that may be safely administered in combination with a fixed regimen of pembrolizumab 200 mg on Day 1 Q3W in patients with Stage IV NSCLC.
- Part B (Expansion Cohort): Dose confirmation of necitumumab in combination with a fixed regimen of pembrolizumab 200 mg on Day 1 Q3W and exploration of clinical antitumor activity in patients with Stage IV NSCLC.
- Part C (Japanese patients): DLT confirmation using the recommended dose from Part A for necitumumab in combination with a fixed regimen of pembrolizumab 200 mg on Day 1 Q3W in Japanese patients with Stage IV NSCLC.

In Part B, approximately 54 patients will be enrolled with an approximately even split between squamous and nonsquamous histology.

[Figure JFCQ.8.1](#) illustrates the study design.

Part A (n = 3-12)

* Part C will first enroll 6 patients. If 2 out of 6 patients experience DLTs, the sponsor will examine the safety data and consult with an external committee as needed. The sponsor will decide if the dose is intolerable, or if additional patients will be enrolled to the same dose level (or lower dose level) for further investigation. If additional patients are needed, 6 additional Japanese patients will be enrolled (to maximum of 12 Japanese patients in Part C).

Abbreviations: D = day; DLT = dose-limiting toxicity; MTD = maximum tolerated dose; n = number of patients; Q3W = every 21 days.

Figure JFCQ.8.1. Illustration of study design.

Part A is a single-arm, dose-escalation study to determine the recommended dose for the expansion cohort (Part B) and Japanese patients (Part C).

Part A:**Cohort 1**

- Pembrolizumab, administered I.V. over 30 minutes (−5 min/+10 min) at an absolute dose of 200 mg on Day 1, followed by
- Necitumumab, administered I.V. over 60 minutes at a dose of 600 mg on Days 1 and 8, Q3W

Cohort 2

- Pembrolizumab, administered I.V. over 30 minutes (–5 min/+10 min) at an absolute dose of 200 mg on Day 1, followed by
- Necitumumab, administered I.V. over 60 minutes at a dose of 800 mg on Days 1 and 8, Q3W

Note: At the time of approval of the JFCQ(c) protocol amendment, all patients who are still on the study will be administered necitumumab I.V. infusion over 60 minutes.

A maximum of 12 evaluable patients with Stage IV NSCLC will be enrolled in Part A. Any patient who is discontinued from the study before completing Cycle 1 will be excluded from the DLT population, unless a DLT was observed. Patients who do not complete Cycle 1 for reason other than DLT will be replaced.

If 1 of 3 patients in cohort 1 experiences a DLT during Cycle 1, 3 additional patients will be enrolled in the cohort. If ≥ 2 of 6 patients experience a DLT in Cohort 1, the study must be discontinued.

Cohort 2 will enroll 6 patients. If ≤ 1 of the 6 patients develops a DLT, Cohort 2 dose will be the recommended Phase 2 dose. If ≥ 2 of the 6 patients experience a DLT in Cohort 2, then the dose in Cohort 1 will be the MTD.

Dose escalation within a cohort will not be permitted. Patients assigned to a cohort dose level will remain at that level throughout the study. Patients who withdraw from the study during the DLT period for reasons other than a treatment-related toxicity may be replaced within the same dose level.

Necitumumab plus pembrolizumab may be continued at the assigned dose level until disease progression, the development of unacceptable toxicity or withdrawal of consent by the patient, or sponsor/investigator decision.

Part B:

Part B will enroll approximately 54 patients. It is a single-arm study to evaluate efficacy and safety of necitumumab in combination with pembrolizumab in patients with Stage IV squamous or nonsquamous NSCLC ([Figure JFCQ.8.1](#)). Patients will be treated with pembrolizumab 200 mg on Day 1 Q3W and the dose of necitumumab identified from Part A of the study on Days 1 and Day 8 Q3W.

Provided there is an acceptable safety profile in Part A of this study, Part B will be initiated, which will include an interim safety analysis after the first 15 evaluable patients have completed 2 cycles of study treatment (or otherwise discontinued study treatment). Patients with squamous and nonsquamous NSCLC from Part A who received the recommended necitumumab dose for Part B will be included in the safety interim analysis.

The final analysis for all outcomes for Part B will be performed approximately 6 months after completing enrollment of the study population.

A treatment cycle will be defined as 21 days. Study therapy, consisting of necitumumab plus pembrolizumab, will continue until there is a radiographic documentation of PD, toxicity requiring cessation, protocol noncompliance, or withdrawal of consent. Discontinuation of treatment may be considered for patients who have attained a confirmed CR that have been treated for at least 24 weeks from Cycle 1 Day 1 with pembrolizumab and necitumumab or pembrolizumab alone and had at least 2 treatments with pembrolizumab with or without necitumumab beyond the date when the initial CR was declared.

Part C:

Part C will only enroll patients from Japan. It is a single-arm study to evaluate safety and tolerability of necitumumab at the recommended dose identified from Part A of the study on Days 1 and Day 8 Q3W in combination with pembrolizumab 200 mg on Day 1 Q3W in Japanese patients with stage IV NSCLC (Figure JFCQ.8.1).

Part C will first enroll 6 patients. If 2 out of 6 patients experience DLTs, the sponsor will examine the safety data and consult with an external committee as needed. The sponsor will decide if the dose is intolerable, or if additional patients will be enrolled to the same dose level (or lower dose level) for further investigation. If additional patients are needed, 6 additional Japanese patients will be enrolled (to maximum of 12 Japanese patients in Part C).

Terms used to describe the periods during the trial are defined below:

- **Baseline:** begins when the ICF is signed and ends at the first study treatment (or at discontinuation, if no treatment is given).
- **Study Period:** begins at the first study treatment and ends at study completion. The study period does not include the continued access period.
 - **Study Treatment Period:** begins at the first study treatment and ends when the patient and the investigator agree that the patient will no longer continue study treatment. The date of this agreement is to be reported on the case report form (CRF) as the Date of Discontinuation from study treatment.
- **Postdiscontinuation Follow-Up:** begins the day after the patient and the investigator agree that the patient will no longer continue study treatment.

Short-term follow-up begins the day after the patient and the investigator agree that the patient will no longer continue study treatment and lasts approximately 30 days.

Long-term follow-up begins the day after short-term follow-up is completed and continues until the patient's death or overall study completion.

[figure not shown]
- **Continued Access Period:** begins after study completion and ends at the end of trial. During the continued access period, patients on study treatment who continue to experience clinical benefit and no undue risks may continue to receive study treatment until one of the criteria for discontinuation is met. The continued access period includes continued access follow-up.

- Continued access follow-up: begins the day after the patient and the investigator agree that the patient will no longer continue treatment in the continued access period and lasts approximately 30 days.

